2.6 Descriptive statistics for secondary outcomes

Means (or medians) and ranges will be reported for continuous outcomes and frequencies will be reported for categorical outcomes.

2.7 Comparative analyses for secondary outcomes

2.7.1 Skin biopsy

Skin biopsy results will be compared between treated skin and untreated skin at each of W2, M3 and M12, for the following variables:

- C7 protein expression by direct immunofluorescence microscopy (DIF)
 - a. C7 IF microscopy

- b. C7 immunofluorescence intensity
- Morphology of anchoring fibrils at the dermal-epidermal junction (DEJ) by transmission electron microscopy (TEM)
 - a. Number of anchoring fibrils
- Vector copy number by quantitative polymerase chain reaction (qPCR)

No hypothesis tests will be performed. Individual listings of all outcomes will be presented (appendix - table 8, 9 and 10). For continuous outcomes, differences in means or medians will be presented. For categorical outcomes, frequencies will be presented for descriptive purposes only (appendix - table 11).

Additionally graphical representations of continuous outcome measures for each patient at different time points will be presented.

2.7.2 Serum test

Serum test results at various time-points post-injections will be compared to baseline, for the following variables:

- Detection of anti-C7 antibodies by enzyme-linked immunosorbent assay (ELISA) (against NC1 and NC2 domains of C7) and indirect immunofluorescence (IIF) at W2, M1, M3, M6 and M12 post-injections:
 - a. C7 ELISA - positive or negative
 - b. Number of C7 ELISA
 - c. IIF – positive or negative
- Detection of T-cell responses to the full length C7 by enzyme-linked immunosorbent spot (ELISPOT) assay at M1, M6 and M12 post-injections:
 - a. C7 ELISPOT - positive or negative
 - b. Number of C7 ELISPOT

No hypothesis tests will be performed. Individual listings of all outcomes will be presented (appendix - table 12, 13 and 14). For continuous outcomes, differences in means or medians will be presented. For categorical outcomes, frequencies will be presented for descriptive purposes only (appendix - table 15).

Additionally graphical representations of continuous outcome measures for each patient at different time points will be presented.

2.8 Interim and final analyses

Adverse events will be monitored throughout the trial by the data monitoring committee (DMC). (See DMC charter)

When all participants complete Visit 7 (Month 6), an interim analysis of the collected data will be performed. There will be another analysis at the end of the trial (12 months after the last participant's cell injections).

2.9 Software

Data management: the BRC secure data management system MedScinet will be used.

Statistical analysis: Stata version 13.1 (Stata Corp LP, Texas, US) or later, will be used for data description and analysis.

Appendix

LIST OF TABLES

Table 2: Summary of recruitment and treatment, by month

Table 3: Study visits completed per patient

Table 4: Baseline demographic and clinical characteristics per patient

Table 5: Treatment related data per patient

Table 6: Summary of adverse events and reactions, including SAEs

Table 7: Adverse events and reactions, including SAEs, per patient

Table 8: Type VII collagen immunofluorescence microscopy and mean immunofluorescence intensity \pm standard error from skin biopsies per patient

Table 9: Morphology of anchoring fibrils at the dermal-epidermal junction (DEJ) by transmission electron microscopy (TEM): anchoring fibrils \pm standard error and integrity from skin biopsies per patient

Table 10: Vector copy number by quantitative polymerase chain reaction (qPCR) from skin biopsies per patient

Table 11: Summary of changes between treated and untreated skin – skin biopsy outcomes

Table 12: Detection of anti-C7 antibodies by enzyme-linked immunosorbent assay (ELISA) (against NC1 and NC2 domains of C7) from serum analysis per patient

Table 13: Detection of anti-C7 antibodies by indirect immunofluorescence (IIF) from serum analysis per patient

Table 14: Detection of T-cell responses to the full length C7 by enzyme-linked immunosorbent spot (ELISPOT) assay from serum analysis per patient

Table 15: Summary of baseline to post-treatment changes – serum analysis outcomes

Table 2: Summary of recruitment and treatment, by month

Month	Recruited*	Skin biopsy/procurement performed	Treated
2015:			
September	xx	xx	xx
October	xx	xx	xx
November	xx	xx	xx
December	xx	xx	xx
2016:			
January	xx	xx	xx
...			
...			
...			
Total			

* Recruited – i.e. consented into screening

Table 3: Study visits completed per patient

Visit Number		V1A	V1B	V2	V3	V4	V5	V6	V7	V8	V9
Timeline of each visit relative to the day of gene-modified fibroblast injections (D0)		Up to 6M3 prior to D0	<3W after 1A	D0	W1 (± 3 D)	W2 (± 3 D)	W4 (± 14 D)	M3 (± 1 M)	M6 (± 1 M)	M9 (± 1 M)	M12 (± 1 M)
Patient ID	Date recruited (V1A) dd/mm/yyyy										
001		X	X	...							
002											
003											
004											
005											
006											
007											
008											
009											
010											

Note: X indicates a completed study visit

Notation: V1A – Screening (up to 6 months prior to treatment day: Day 0); V1B – Screening and skin procurement (<3 weeks after V1A); V2 (D0) – Intradermal injections of gene-modified autologous fibroblasts; V3 (W1) – 1 week after the injections ± 3 days; V4 (W2) – 2 weeks after the injections ± 3 days; V5 (W4) – 4 weeks after the injections ± 14 days; V6 (M3) – 3 months after the injections ± 1 month; V7 (M6) – 6 months after the injections ± 1 month; V8 (M9) – 9 months after the injections ± 1 month; V9 (M12) – 12 months after the injections ± 1 month

Table 4: Baseline demographic and clinical characteristics per patient

		Patient ID									
		001	002	003	004	005	006	007	008	009	010
Demographics											
Age (years)		XX.X									
Sex (Male/Female)											
Ethnicity											
BMI (kg/m ²)		XX.X									
RDEB characteristics											
Type of RDEB ¹											
COL7A1 mutations											
C7 immunofluorescence											
	C7 IF microscopy ²										
	C7 MII ± SE ³	XX.X ±XX.X									
Anchoring fibrils											
	AF number ± SE ⁴	XX.X ±XX.X									
	Integrity (free text)										
Vector copy number		XX.X									
BEBSS		XX.X									
Immune profile											
C7 IIF											
	(Pos/Neg)										
C7 ELISA											
	(Pos/Neg)										
	Titres (U)	XX.X									
C7 ELISPOT											
	(Pos/Neg)										
	Number of spots	XX.X									
Patient Clinical Information											
Suitable site for injections											
Significant co-morbidities											
Blood test results											
Hb (g/L)		XX.X									
MCV (fl)		XX.X									
WCC (x10 ⁹)		XX.X									
Neutrophils (g/L)		XX.X									
Platelets (x10 ⁹ g/L)		XX.X									
CRP (mg/L)		XX.X									
ESR (mm/hr)		XX.X									
Sodium (mmol/L)		XX.X									
Potassium (mmol/L)		XX.X									
Creatinine (g/L)		XX.X									
Bilirubin (μmol/L)		XX.X									
ALP (iu/L)		XX.X									
ALT (iu/L)		XX.X									
Albumin (g/L)		XX.X									

Acronyms: RDEB=recessive dystrophic epidermolysis bullosa; IF= immunofluorescence; MII= mean immunofluorescence intensity; SE=standard error; AF=anchoring fibrils; BEBSS=Birmingham epidermolysis bullosa severity score (0-100); IIF=indirect immunofluorescence; ELISA= enzyme-linked immunosorbent assay; ELISPOT=enzyme-linked immunosorbent spot; Hb=Haemoglobin; MCV=mean corpuscular volume;

WCC=White cell count; CRP=C-reactive protein; ESR=Erythrocyte sedimentation rate; ALP=alkaline phosphatase; and ALT=alanine aminotransferrase.

¹Type of RDEB: *GS=Generalised severe, GI=Generalised intermediate, In=Inversa, Lo=Localised, PT=Pretibial, Pru=Pruriginosa, Cen=Centripetalis, BDNB=Bullous dermolysis of the new born.*

²*C7 IF microscopy: CD=Complete deficiency, PD=Partial deficiency, ND=No deficiency.*

³*C7 MII ± SE = Type VII collagen mean immunofluorescence intensity ± standard error*

⁴*AF ± SE = anchoring fibrils ± standard error*

Note: All baseline values are taken from visits 1A or 1B which are up to 6 months and 6 weeks prior to administration of IMP, respectively. With the exception of the ELISPOT values which are taken at visit 2 prior to administration of the IMP.

Table 5: Treatment related data per patient

Patient ID	Time from treatment of previous patient (days)	Date of treatment	Site of treatment	Cell numbers injected in Square 1 (x10 ⁶ cells in 0.25ml of 0.9% saline)	Cell numbers injected in Square 2 (x10 ⁶ cells in 0.25ml of 0.9% saline)	Cell numbers injected in Square 3 (x10 ⁶ cells in 0.25ml of 0.9% saline)
001	xx	dd/mm/yyyy		xx.x	xx.x	xx.x
002						
003						
004						
005						
006						
007						
008						
009						
010						

Table 6: Summary of adverse events and reactions, including SAEs

		Number of events nAE	Number of patients n
Overall			
Adverse events (AE)		xx	xx
Serious adverse events (SAE)		xx	xx
Suspected unexpected serious adverse reactions (SUSAR)		xx	xx
Serious adverse reactions (SAR)		xx	xx
Severity Grade¹			
1		xx	xx
2		xx	xx
3		xx	xx
4		xx	xx
5		xx	xx

NOTE: nAE = number of adverse events (or SAE/SUSAR/SAR); n =number of patients experiencing at least one event.

¹ **Severity grade:** 1=mild: awareness of signs or symptoms, but easily tolerated; 2=moderate: uncomfortable enough to cause interference with usual activity; 3=severe: incapacity with inability to work or do usual activity; 4=life-threatening; 5=death.

Table 7: Adverse events and reactions, including SAEs, per patient

Patient ID	Event	Days from treatment to onset	Start date dd/mm/yyyy	End date dd/mm/yyyy	Serious? ¹ Y/N	Severity Grade ² (1-5)	Causality ³	Outcome ⁴	Treatment (free text)	Medications received if any

¹**Serious:** yes/no. *NOTE: If yes, qualifies an AE/R as Serious (SAE/R)*

²**Severity grade:** 1=mild: awareness of signs or symptoms, but easily tolerated; 2=moderate: uncomfortable enough to cause interference with usual activity; 3=severe: incapacity with inability to work or do usual activity; 4=life-threatening; 5=death;

³**Causality:** unlikely to be related / possibly related / probably related / definitely related. *NOTE: Causality of 'possibly' or greater qualifies an AE as an Adverse Reaction (AR).*

⁴**Outcome:** fully recovered/recovered with sequelae/no recovery/fatal

Table 8: Type VII collagen immunofluorescence microscopy and mean immunofluorescence intensity \pm standard error from skin biopsies per patient

Patient ID	C7 IF	Baseline		Week 2		Month 3		Month 12	
		Treated	Untreated	Treated	Untreated	Treated	Untreated	Treated	Untreated
001	Microscopy ¹								
	Intensity ²	xx.x \pm xx.x							
002	Microscopy ¹								
	Intensity ²	xx.x \pm xx.x							
003	Microscopy ¹								
	Intensity ²	xx.x \pm xx.x							
004	Microscopy ¹								
	Intensity ²	xx.x \pm xx.x							
005	Microscopy ¹								
	Intensity ²	xx.x \pm xx.x							
006	Microscopy ¹								
	Intensity ²	xx.x \pm xx.x							
007	Microscopy ¹								
	Intensity ²	xx.x \pm xx.x							
008	Microscopy ¹								
	Intensity ²	xx.x \pm xx.x							
009	Microscopy ¹								
	Intensity ²	xx.x \pm xx.x							
010	Microscopy ¹								
	Intensity ²	xx.x \pm xx.x							

Acronyms: IF = immunofluorescence.

¹C7 IF microscopy: CD=Complete deficiency, PD=Partial deficiency, ND=No deficiency.

²C7 MII \pm SE = Type VII collagen mean immunofluorescence intensity \pm standard error

Table 9: Morphology of anchoring fibrils at the dermal-epidermal junction (DEJ) by transmission electron microscopy (TEM): anchoring fibrils \pm standard error and integrity from skin biopsies per patient

Patient ID		Baseline	Week 2		Month 3		Month 12	
			Treated	Untreated	Treated	Untreated	Treated	Untreated
001	AF number ¹	xx.x \pm xx.x						
	Integrity							
002	AF number ¹	xx.x \pm xx.x						
	Integrity							
003	AF number ¹	xx.x \pm xx.x						
	Integrity							
004	AF number ¹	xx.x \pm xx.x						
	Integrity							
005	AF number ¹	xx.x \pm xx.x						
	Integrity							
006	AF number ¹	xx.x \pm xx.x						
	Integrity							
007	AF number ¹	xx.x \pm xx.x						
	Integrity							
008	AF number ¹	xx.x \pm xx.x						
	Integrity							
009	AF number ¹	xx.x \pm xx.x						
	Integrity							
010	AF number ¹	xx.x \pm xx.x						
	Integrity							

Acronyms: AF = anchoring fibrils.

¹AF \pm SE = anchoring fibrils \pm standard error.

Table 10: Vector copy number by quantitative polymerase chain reaction (qPCR) from skin biopsies per patient

Patient ID	Baseline	Week2		Month 3		Month 12	
		Treated	Untreated	Treated	Untreated	Treated	Untreated
001	XX.X	XX.X	XX.X	XX.X	XX.X	XX.X	XX.X
002	XX.X	XX.X	XX.X	XX.X	XX.X	XX.X	XX.X
003	XX.X	XX.X	XX.X	XX.X	XX.X	XX.X	XX.X
004	XX.X	XX.X	XX.X	XX.X	XX.X	XX.X	XX.X
005	XX.X	XX.X	XX.X	XX.X	XX.X	XX.X	XX.X
006	XX.X	XX.X	XX.X	XX.X	XX.X	XX.X	XX.X
007	XX.X	XX.X	XX.X	XX.X	XX.X	XX.X	XX.X
008	XX.X	XX.X	XX.X	XX.X	XX.X	XX.X	XX.X
009	XX.X	XX.X	XX.X	XX.X	XX.X	XX.X	XX.X
010	XX.X	XX.X	XX.X	XX.X	XX.X	XX.X	XX.X

Table 11: Summary of changes between treated and untreated skin – skin biopsy outcomes

		Treated skin	Untreated skin
		N	N
C7 IF microscopy			
Baseline			
	Complete deficiency		xx
	Partial deficiency		xx
	No deficiency		xx
Week 2			
	Complete deficiency	xx	xx
	Partial deficiency	xx	xx
	No deficiency	xx	xx
Month 3			
	Complete deficiency	xx	xx
	Partial deficiency	xx	xx
	No deficiency	xx	xx
Month 12			
	Complete deficiency	xx	xx
	Partial deficiency	xx	xx
	No deficiency	xx	xx
C7 mean immunofluorescence intensity			
Baseline, mean (range)			xx.x (xx.x, xx.x)
W2, mean (range)		xx.x (xx.x, xx.x)	xx.x (xx.x, xx.x)
Change from W2 to baseline			
	Mean (range)	xx.x (xx.x, xx.x)	xx.x (xx.x, xx.x)
	Difference		xx.x
M3, mean (range)		xx.x (xx.x, xx.x)	xx.x (xx.x, xx.x)
Change from M3 to baseline			
	Mean (range)	xx.x (xx.x, xx.x)	xx.x (xx.x, xx.x)
	Difference		xx.x
M12, mean (range)		xx.x (xx.x, xx.x)	xx.x (xx.x, xx.x)
Change from M12 to baseline			
	Mean (range)	xx.x (xx.x, xx.x)	xx.x (xx.x, xx.x)
	Difference		xx.x
Morphology of anchoring fibrils at the dermal-epidermal junction (DEJ) by transmission electron microscopy (TEM)			
Number of anchoring fibrils			
Baseline, mean (range)			xx.x (xx.x, xx.x)
W2, mean (range)		xx.x (xx.x, xx.x)	xx.x (xx.x, xx.x)
Change from W2 to baseline			
	Mean (range)	xx.x (xx.x, xx.x)	xx.x (xx.x, xx.x)
	Difference		xx.x
M3, mean (range)		xx.x (xx.x, xx.x)	xx.x (xx.x, xx.x)
Change from M3 to baseline			
	Mean (range)	xx.x (xx.x, xx.x)	xx.x (xx.x, xx.x)
	Difference		xx.x
M12, mean (range)		xx.x (xx.x, xx.x)	xx.x (xx.x, xx.x)
Change from M12 to baseline			
	Mean (range)	xx.x (xx.x, xx.x)	xx.x (xx.x, xx.x)
	Difference		xx.x

Vector copy number by quantitative polymerase chain reaction (qPCR)			
Baseline, mean (range)		xx.x (xx.x, xx.x)	
W2, mean (range)	xx.x (xx.x, xx.x)	xx.x (xx.x, xx.x)	
Change from W2 to baseline			
	Mean (range)	xx.x (xx.x, xx.x)	xx.x (xx.x, xx.x)
	Difference		xx.x
M3, mean (range)	xx.x (xx.x, xx.x)	xx.x (xx.x, xx.x)	
Change from M3 to baseline			
	Mean (range)	xx.x (xx.x, xx.x)	xx.x (xx.x, xx.x)
	Difference		xx.x
M12, mean (range)	xx.x (xx.x, xx.x)	xx.x (xx.x, xx.x)	
Change from M12 to baseline			
	Mean (range)	xx.x (xx.x, xx.x)	xx.x (xx.x, xx.x)
	Difference		xx.x

Acronyms: IF = immunofluorescence.

Table 12: Detection of anti-C7 antibodies by enzyme-linked immunosorbent assay (ELISA) (against NC1 and NC2 domains of C7) from serum analysis per patient

		Baseline	Week 2	Month 1	Month 3	Month 6	Month 12
Patient ID							
001	C7 ELISA ¹						
	C7 titre	xx.x	xx.x	xx.x	xx.x	xx.x	xx.x
002	C7 ELISA ¹						
	C7 titre	xx.x	xx.x	xx.x	xx.x	xx.x	xx.x
003	C7 ELISA ¹						
	C7 titre	xx.x	xx.x	xx.x	xx.x	xx.x	xx.x
004	C7 ELISA ¹						
	C7 titre	xx.x	xx.x	xx.x	xx.x	xx.x	xx.x
005	C7 ELISA ¹						
	C7 titre	xx.x	xx.x	xx.x	xx.x	xx.x	xx.x
006	C7 ELISA ¹						
	C7 titre	xx.x	xx.x	xx.x	xx.x	xx.x	xx.x
007	C7 ELISA ¹						
	C7 titre	xx.x	xx.x	xx.x	xx.x	xx.x	xx.x
008	C7 ELISA ¹						
	C7 titre	xx.x	xx.x	xx.x	xx.x	xx.x	xx.x
009	C7 ELISA ¹						
	C7 titre	xx.x	xx.x	xx.x	xx.x	xx.x	xx.x
010	C7 ELISA ¹						
	C7 titre	xx.x	xx.x	xx.x	xx.x	xx.x	xx.x

Acronyms: ELISA = enzyme-linked immunosorbent assay.

¹ C7 ELISA: positive, negative.

Table 13: Detection of anti-C7 antibodies by indirect immunofluorescence (IIF) from serum analysis per patient

Patient ID		Baseline	Week 2	Month 1	Month 3	Month 6	Month 12
001	C7 IIF ¹						
002	C7 IIF ¹						
003	C7 IIF ¹						
004	C7 IIF ¹						
005	C7 IIF ¹						
006	C7 IIF ¹						
007	C7 IIF ¹						
008	C7 IIF ¹						
009	C7 IIF ¹						
010	C7 IIF ¹						

Acronyms: IIF=indirect immunofluorescence.

¹ C7 IIF: positive, negative.

Table 14: Detection of T-cell responses to the full length C7 by enzyme-linked immunosorbent spot (ELISPOT) assay from serum analysis per patient

Patient ID		Baseline	Month 1	Month 6	Month 12
001	C7 ELISPOT ¹				
	No. of spots	xx.x	xx.x	xx.x	xx.x
002	C7 ELISPOT ¹				
	No. of spots	xx.x	xx.x	xx.x	xx.x
003	C7 ELISPOT ¹				
	No. of spots	xx.x	xx.x	xx.x	xx.x
004	C7 ELISPOT ¹				
	No. of spots	xx.x	xx.x	xx.x	xx.x
005	C7 ELISPOT ¹				
	No. of spots	xx.x	xx.x	xx.x	xx.x
006	C7 ELISPOT ¹				
	No. of spots	xx.x	xx.x	xx.x	xx.x
007	C7 ELISPOT ¹				
	No. of spots	xx.x	xx.x	xx.x	xx.x
008	C7 ELISPOT ¹				
	No. of spots	xx.x	xx.x	xx.x	xx.x
009	C7 ELISPOT ¹				
	No. of spots	xx.x	xx.x	xx.x	xx.x
010	C7 ELISPOT ¹				
	No. of spots	xx.x	xx.x	xx.x	xx.x

Acronyms: ELISPOT=enzyme-linked immunosorbent spot.

¹ C7 ELISPOT: positive, negative.

Table 15: Summary of baseline to post-treatment changes – serum analysis outcomes

			Baseline to post-treatment difference
	Positive N	Negative N	
Detection of anti-C7 antibodies by enzyme-linked immunosorbent assay (ELISA) (against NC1 and NC2 domains of C7) and indirect immunofluorescence (IIF)			
C7 ELISA			
Baseline	xx	xx	-
Week 2	xx	xx	-
Month 1	xx	xx	-
Month 3	xx	xx	-
Month 6	xx	xx	-
Month 12	xx	xx	-
C7 ELISA titre			
Baseline, mean (range)	xx.x (xx.x, xx.x)		-
Week 2, mean (range)	xx.x (xx.x, xx.x)	xx.x (xx.x, xx.x)	
Month 1, mean (range)	xx.x (xx.x, xx.x)	xx.x (xx.x, xx.x)	
Month 3, mean (range)	xx.x (xx.x, xx.x)	xx.x (xx.x, xx.x)	
Month 6, mean (range)	xx.x (xx.x, xx.x)	xx.x (xx.x, xx.x)	
Month 12, mean (range)	xx.x (xx.x, xx.x)	xx.x (xx.x, xx.x)	
C7 IIF			
Baseline	xx	xx	-
Week 2	xx	xx	-
Month 1	xx	xx	-
Month 3	xx	xx	-
Month 6	xx	xx	-
Month 12	xx	xx	-
Detection of T-cell responses to the full length C7 by enzyme-linked immunosorbent spot (ELISPOT) assay			
C7 ELISPOT			
Baseline	xx	xx	-
Month 1	xx	xx	-
Month 6	xx	xx	-
Month 12	xx	xx	-
Number of spots			
Baseline, mean (range)	xx.x (xx.x, xx.x)		-
Month 1, mean (range)	xx.x (xx.x, xx.x)	xx.x (xx.x, xx.x)	
Month 6, mean (range)	xx.x (xx.x, xx.x)	xx.x (xx.x, xx.x)	
Month 12, mean (range)	xx.x (xx.x, xx.x)	xx.x (xx.x, xx.x)	

Acronyms: ELISA = enzyme-linked immunosorbent assay; IIF = indirect immunofluorescence; and

ELISPOT = enzyme-linked immunosorbent spot.

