5.9 Subject compliance

The IMP will be administered to the trial participants attending St John's Institute of Dermatology at GSTT in the designated Clinical Research Facilities, [name]. Non compliance issues are not expected as the treatment is administered in hospital setting by a member of the research team. Skin biopsies and blood tests will also be performed by a member or members of the clinical team. However, because the study population involves adults with a severe blistering skin disease, if a blood test is unobtainable at a particular time, the investigators may use a blood sample obtained at a more convenient time (but chronologically related). Participants will be assessed for any adverse events and concomitant medications at each visit from V1B but otherwise, no assessments are scheduled to be performed by study subjects

at home so no subject compliance issues are expected. Support and guidance will be provided by members of the clinical research team as required.

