8.3 Procedures for assessing efficacy parameters

Clinical assessment: Review of adverse events and concomitant medications will be performed at each visit from V1B. Physical examination, vital signs and clinical

photography of the injection sites will be performed at each visit. BEBS score will be documented at screening, W2, M3 and M12. Efforts will be made for the clinical assessment to be performed by the same assessor for each participant throughout the trial to minimise inter-observer variations.

Biochemical analysis: Routine blood analysis including FBC, U&Es, LFTs, ESR and CRP will be measured at screening, D0, W2, W4, M3, M6 and M12 to monitor any potential systemic adverse effects. At the screening visits, virology tests for HIV, HepBcAb, HepBsAg, HepC IgG, HTLV1&2 and *Treponema pallidum* serology will be performed to screen for blood borne viral infections and treated as per GSTT guidelines. Analysis of antibodies for C7 and IIF will be performed both prior to and after IMP administration (screening, W2, W4, M3, M6 and M12) in order to detect any potential development of EB acquisita in participants with RDEB as a potential adverse effect of introducing new C7 expression from the gene-modified autologous fibroblasts. ELISPOT assay for detection of T-cell responses to the full length C7 will be performed at screening, W4, M6 and M12.

Skin Ultrastructural Analysis: Skin biopsies will be taken at four time points (screening, W2, M3 and M12) for C7 IF microscopy to assess a change in the level of C7 expression. This will be correlated with the presence and morphology of anchoring fibrils at the DEJ as assessed by TEM.

Vector copy number (VCN) and COL7A1 gene expression: Real-time polymerase chain reaction (qPCR) will be used to analyse vector copy in the skin biopsy of the cell injection sites at W2, M3 and M12.

Histology: Skin histology will be used to analyse the difference in the morphology of DEJ between treated and untreated skin at W2, M3 and M12.

9 Assessment of Safety

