9.2 Specification, timing and recording of safety parameters

Adverse events (AEs): All researchers involved in this trial must be familiar with the assessment of safety for the trial. Researchers are defined as any clinical researcher, investigator, research nurse or other personnel member conducting trial related clinical research activity. It is imperative that all investigators have a thorough understanding of anticipated AEs and the reporting process of these events. All AEs will be recorded in accordance with ICH GCP, EU directives and King's Health Partners Clinical Trials Office (KHP-CTO) SOPs.

Medical history: A full medical history will be taken from the patient by a member of the clinical team during the screening visit. This ensures that the study participants satisfy the eligibility criteria and do not have any medical conditions that would make it

inappropriate for them to participate in the study. All known medical history since birth, including ongoing conditions, will be recorded in the CRF, together with any other clinically important findings that the Investigator considers relevant to the study.

Physical examination: A physical examination of each subject will be conducted by the Investigator at all trial visits. All abnormal findings (including gastrostomies and surgical scars) will be documented at screening. Any changes that occur during the study will be documented.

Vital signs: Vital signs (heart rate, blood pressure, respiratory rate and temperature) will be measured at screening, day 0 (treatment day), and at every follow-up visit.

Serum analyses: Routine blood analysis including FBC, U&Es, LFTs, ESR and CRP will be measured at screening, D0, W2, W4, M3, M6 and M12 to monitor any potential systemic adverse effects. Analysis of antibodies for C7 and IIF will be performed both prior to and after IMP administration (screening, W2, W4, M3, M6 and M12) in order to detect any potential development of EB acquisita in participants with RDEB as a potential adverse effect of introducing new C7 expression from the gene-modified autologous fibroblasts. ELISPOT assay for detection of T-cell responses to the full length C7 will be performed at screening, W4, M6 and M12.

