1.7 Procedures by visit

Visit number	V1A	V1B	V2	V3	V4	V5	V6	V7	V8	V9
Timeline of each visit relative to the day of gene-modified fibroblast injections (D0)	Up to 6M prior to D0	At least 6W prior to D0	D0	W1 (±3D)	W2 (±3D)	W4 (±14D)	M3 (±1M)	M6 (±1M)	M9 (±1M)	M12 (±1M)
Approximate duration of each visit (hours)	2	2	1.5	1.5	2	1.5	2	1.5	1.5	2
Informed consent	X									
Inclusion / exclusion	X	X								
Demographics	X									
Medical history	X									
Vital signs	X	X	X	X	X	X	X	X	X	X
Physical examination	X	X	X	X	X	X	X	X	X	X
Serum pregnancy test for female participants with child-bearing potential (if serum is not obtainable, urine pregnancy test may be used)	X	X	X							
^a BEBS Score	X				X		X			X
^b Clinical photography	X	X	X	X	X	X	X	X	X	X
Blood samples	^c Basic bloods		X	X	X	X	X	X		X
	^d Virology		X	X						

Visit number		V1A	V1B	V2	V3	V4	V5	V6	V7	V8	V9
Timeline of each visit relative to the day of gene-modified fibroblast injections (D0)		Up to 6M prior to D0	At least 6W prior to D0	D0	W1 (±3D)	W2 (±3D)	W4 (±14D)	M3 (±1M)	M6 (±1M)	M9 (±1M)	M12 (±1M)
	C7 ELISA & IIF	X				X	X	X	X		X
	ELISPOT			X			X		X		X
	^e RCL	X				X	X	X			X
Skin biopsies	C7 IF microscopy & TEM		X			X		X			X
	^f qPCR		X			X		X			X
	^g Integration site analysis		X			X		X			X
Skin procurement (1x6mm)	Tissue culture for IMP production		X								
^h Intradermal injections of IMP				X							
Adverse event(s) assessment			X	X	X	X	X	X	X	X	
Concomitant medications assessment			X	X	X	X	X	X	X	X	

Table 1: LENTICOL-F trial flowchart with details of interventions at each visit.

Abbreviations: V=Visit; D=Day; W=Week; M=Month.

Consent will be obtained at each visit. On Day 0, your vital signs will be monitored every 15mins for 30mins after the gene-modified fibroblast injections. There will be one-off readings of the vital signs on the rest of the other visits during the study. Historical samples/ results may be used for C7 ELISA & IIF, ELISPOT, C7 IF microscopy & TEM. Historical virology results performed within the last 3 months may be used. NB: If W2 and M3 skin biopsy results are negative then M12 biopsy may not be performed.

^aBirmingham Epidermolysis Bullosa Severity Score;

^bClinical photography of potential injection sites over an area of the intact skin will be taken at screening on visit 1, post-IMP injections on visit 2 and at each visit thereafter;

^cIncludes FBC, U&Es, LFTs, ESR and CRP;

^dIncludes HIV, HepBcAb, HepBsAg, HepC IgG, HTLV 1&2 and Treponema pallidum serology;

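### Anti-C7 ELISA and IIF have no day-0 sample, so a positive first seen at week 2 is of uncertain timing relative to dosing; ELISPOT already has a planned pre-dose baseline

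*SAP*

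**What the plan says.** Both schedules of procedures (protocol 7.4, Table 2; SAP 1.7, Table 1) place C7 ELISA and IIF at V1A, W2, W4, M3, M6 and M12, and leave V2 (day 0) blank. Protocol 8.3 and 9.2 give the same list, starting at screening.

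The timing of V1A follows from three statements:
- Protocol 7.1 and SAP 1.6 allow V1A up to 6 months before day 0. Protocol 6.6 says up to 4 months.
- V1B is "At least 6W prior to D0" in both schedules.
- SAP Table 3 gives the order of the two visits: "V1B – Screening and skin procurement (<3 weeks after V1A".

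The footnote to each schedule adds: "Historical samples/ results may be used for C7 ELISA & IIF, ELISPOT, C7 IF microscopy & TEM". It gives no age limit, although the next sentence limits historical virology to the last 3 months. Protocol 5.9 further provides that "if a blood test is unobtainable at a particular time, the investigators may use a blood sample obtained at a more convenient time", as long as the sample is chronologically related.

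For the analysis, the SAP Table 4 note states "All baseline values are taken from visits 1A or 1B which are up to 6 months and 6 weeks prior to administration of IMP", and then "With the exception of the ELISPOT values which are taken at visit 2 prior to administration of the IMP". SAP 2.7.2 and Table 15 compare each post-injection serum result with that baseline.

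**The concern.** Protocol 8.3 gives the purpose of the ELISA and IIF series: it is done "in order to detect any potential development of EB acquisita in participants with RDEB as a potential adverse effect". Protocol 9.1 relies on the same tests to watch for a delayed immune response to the product, and secondary objective ii in SAP 1.1.2 is framed as a comparison with baseline.

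The trial has one arm. The biopsy outcomes have an untreated site for comparison at each visit; serum has only the participant's own pre-dose value. If that value is weeks or months old at dosing, a change first seen at W2 spans both a pre-dose and a post-dose period, and the planned tables do not separate them. With 5–10 participants, a single such conversion is 10–20% of the sample.

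A current pre-dose value would also help because exclusion V requires both tests to be positive. A participant positive on only one can be enrolled.

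**Working it through.** **The plan's own figure.** The documents give no number on this point. Their one statistical figure is the exact 95% interval for 0 adverse reactions in 10. It reproduces, 1 − 0.025^(1/10) = 30.8%, stated as 31%, but nothing here depends on it.

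**Inputs.**
- b, the age of the baseline at dosing. V1B is at least 6 weeks before day 0 and follows V1A, so a scheduled V1A sample has b of at least 42 days. The upper limit is 6 months = 6 × 30.4375 = 182.6 days, or 4 months = 4 × 30.4375 = 121.75 days under protocol 6.6.
- p, the day of the first post-dose sample. W2 is day 14 ± 3, so p runs from 11 to 17.

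**Formula.** Share of the baseline-to-W2 interval that lies before dosing = b / (b + p).

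| Case | b (days) | p (days) | Pre-dose share |
|---|---|---|---|
| Lowest, across the W2 window | 42 | 17 | 42/59 = 71.2% |
| Highest, across the W2 window | 182.6 | 11 | 182.6/193.6 = 94.3% |
| Latest V1A, nominal W2 | 42 | 14 | 42/56 = 75.0% |
| V1B at its 6-week minimum, V1A 3 weeks earlier | 63 | 14 | 63/77 = 81.8% |
| 4-month limit, nominal W2 | 121.75 | 14 | 121.75/135.75 = 89.7% |
| 6-month limit, nominal W2 | 182.6 | 14 | 182.6/196.6 = 92.9% |
| Day-0 baseline | 0 | 11–17 | 0% |

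The interval in which a conversion first seen at W2 could have occurred is 42 + 11 = 53 days at its shortest and 182.6 + 17 = about 200 days at its longest. With a day-0 sample it is 11–17 days. If a historical result serves as baseline, the documents set no upper limit.

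**Later visits.** Table 15 takes titre differences from the same baseline at every visit, so each difference includes the pre-dose gap. Because b / (b + p) falls as p grows, the share is smaller at later visits. I give no ranges there: the windows are wide (± 14 days at W4, ± 1 month from M3) and the screening limit is stated two ways.

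**Is day-0 serum available elsewhere?** None is planned. The schedules archive blood for replication-competent lentivirus at V1A, W2, W4, M3 and M12, not at day 0. Blood is nevertheless drawn at V2: protocol Table 2 marks basic bloods and ELISPOT there.

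**Can a reader work out the baseline's age?** For a scheduled sample, yes: SAP Table 3 lists the V1A date and Table 5 the treatment date. For a substituted or historical sample, no: Tables 4, 12 and 13 have no field for sample date or source.

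**The case against.** The strongest reply is that little hangs on this. The outcome is secondary, no hypothesis test is planned, and causality of a clinical event is judged event by event rather than computed from the ELISA baseline. No sample size, interval or stated stopping criterion depends on it. V1A is also the right time for the eligibility test, since exclusion V should be settled before biopsy and manufacture. All of this stands, and it keeps the point minor. It does not explain why ELISPOT has a pre-dose baseline in the SAP and the other two immune assays do not.

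A reader might infer several stronger claims that the documents do not support:
- **That a W2 positive can never be attributed to treatment.** SAP 2.7.2 plans individual listings and graphs over time, and Table 12 gives titres through M12. A titre that rises or stays flat after W2 bears on timing, though not conclusively. Uncertain is the right word.
- **That later conversions share the problem.** A participant negative at W2 and positive afterwards converted after dosing.
- **That historical baselines are undated.** The footnotes set no age limit; they do not say dates are unknown. Nor do they say that a historical result becomes the analysis baseline. The Table 4 note names only V1A or V1B, so they may be meant only to replace a screening test.
- **That ELISPOT is secure.** Its day-0 baseline is planned, but the same footnote allows historical ELISPOT results.
- **That background conversion is known to be rare.** Protocol 3.8 reports none of five RDEB subjects with circulating anti-C7 antibodies three months after fibroblast injections. With 0 of 5 the exact 95% upper limit is 1 − 0.025^(1/5) = 52%, and those cells are not described as gene-modified. It supports little either way.

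**Conclusion.** The point holds as a minor design weakness. For a participant negative at baseline and first positive at W2, the planned data leave the timing relative to dosing uncertain, because 71%–94% of the interval is pre-dose (at most about 90% at day 14 under the 4-month limit). Titre changes at later visits carry the same gap in a smaller share.

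This assumes a scheduled V1A sample, the order of visits in SAP Table 3 and a W2 sample inside its window. A sample substituted under protocol 5.9 could be older or newer.

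The percentages might be read as the chance of wrongly blaming or clearing the product. They are not: they are shares of elapsed time. The documents give no background conversion rate and no evidence of pre-dose titre drift, so no probability of misattribution can be stated.

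**What to change.** 1. Add C7 ELISA and IIF to the existing day-0 pre-dose draw (protocol 7.4, 8.3 and 9.2; SAP 1.7), and name that sample as the analysis baseline for SAP Tables 4, 12, 13 and 15. Keep the V1A test for eligibility; the day-0 result need not decide same-day eligibility.
2. If day-0 blood cannot be obtained, use the latest pre-dose sample.
3. Add to Tables 12 and 13 the date of the baseline serum and its source: scheduled, substituted or historical. Fill this in for anyone already dosed.

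The cost is one extra tube per participant at a draw already made, 5–10 additional ELISA/IIF assays in total, and two fields in two tables. No visit is added.

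Two clerical corrections are separate from the argument above. The Table 4 note turns V1B's 6-week minimum into a maximum and should follow the schedules. Protocol 9.2 states "ELISPOT assay for detection of T-cell responses to the full length C7 will be performed at screening, W4, M6 and M12", and 8.3 says the same; the screening entry should read day 0 pre-dose, to agree with the schedules and the SAP note.
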